## 11.3. Efficacy Analyses

### 11.3.1. Analysis of the Primary Endpoint

The primary objective of this study is to test the hypothesis that either dose regimen evaluated for atabecestat will slow cognitive decline compared with placebo, as measured by the primary endpoint of the PACC change from baseline at Month 54 (see Section 9.3.1).

The primary estimand, the main clinical quantity of interest to be estimated in the study, is defined by the difference in means versus placebo for the primary endpoint in the specified population under the following postrandomization measure of intervention:

- **Population:** amyloid-positive subjects who are asymptomatic at risk for developing Alzheimer's dementia
- **Endpoint:** The Month 54 (Year 4.5) PACC change score (as defined in Section 9.3.1)
- **Measure of Intervention:** the effect of the initially randomized treatment regardless of treatment compliance or initiation of any Alzheimer adjunctive therapy.

The primary analysis will be based on the intent-to-treat analysis set, which includes all randomized subjects. The analysis of the PACC change score will only include subjects for whom the PACC change score is non-missing at least 1 postbaseline time point. Measurements collected after initiation of any Alzheimer adjunctive therapy will be included in the analysis for the primary estimand. Measurements collected after treatment discontinuations due to reasons potentially related to treatment (eg, treatment-related adverse events or lack of efficacy) will also be included in the analysis of the primary estimand. However, measurements collected after treatment discontinuations due to events that are clearly not treatment-related (eg, life events such as relocation, loss of transportation, loss of informant) will not be included in the analysis of the primary estimand.

A mixed effect model for repeated measurement (MMRM) analysis will be performed to assess the treatment effect. The change from baseline in PACC at each visit that the endpoint is measured will be the dependent variable. Visits scheduled for the measure will be treated as a categorical variable with values equal to the visit numbers. An unstructured covariance structure will be assumed. The model for the fixed effects will include the following terms: baseline of the endpoint measure, treatment group, visit, treatment-by-visit interaction, age, sex, education, hippocampal volume, country, and *APOE*  $\epsilon 4$  carrier status.

The null hypothesis is that there is no treatment difference between either dose of atabecestat and placebo for the primary endpoint. The estimated treatment effects at 4.5 years will be compared using the appropriate contrasts based on the MMRM at a 2-sided 0.05 significance level. The Kenward-Roger approximation will be used to estimate the denominator degrees of freedom. If the unstructured covariance structure matrix results in a lack of convergence, an alternative covariance structure will be used. The details will be specified in the SAP.

Supplementary analyses may be performed to further characterize the treatment effect on the primary endpoint.

### **11.3.2. Analysis of the Secondary Endpoints**

The secondary endpoints are defined in Section 9.3.2. The key secondary endpoint in this study is the CFI. Other secondary endpoints include ADCS-ADL-PI, RBANS, CDR-SB, and NAB-DLTs for Memory and Attention.

All secondary endpoint analyses will be performed in the intent-to-treat analysis set. The change from baseline in CFI total score will be analyzed using an MMRM analysis. The change from baseline score at each visit will be the dependent variable. Visits scheduled for the measure will be treated as a categorical variable. An unstructured covariance structure will be assumed. The model for the fixed effects will include the following terms: baseline of the endpoint measure, treatment group, visit, treatment-by-visit interaction, age, sex, education, hippocampal volume, country and *APOE*  $\epsilon 4$  carrier status. If the unstructured covariance structure matrix results in a lack of convergence, an alternative covariance structure will be used.

For each of the other secondary efficacy endpoints, the change from baseline score will be similarly analyzed as above.

Descriptive statistics and evaluation of the CFI-a's ability to measure change over time will be described in the SAP.

Supplementary analyses may be performed to further characterize the treatment effect on the secondary endpoints. Data from the other clinical scales will generally be summarized descriptively by treatment group. Additional details will be provided in the SAP.

### **11.3.3. Multiple Comparison Adjustment**

Statistical adjustment will be made to account for multiplicity due to multiple dose comparisons for the primary endpoint and the key secondary endpoint (Section 11.3.1 and Section 11.3.2). To control the Type I error a 2-stage gatekeeping strategy will be employed. In the first stage, the atabecestat dose arms will be compared with placebo on the primary efficacy endpoint using a truncated Hochberg procedure with a 2-sided  $\alpha = 0.05$  and truncation parameter  $\lambda = 0.5$ . If both arms are superior to placebo, both arms will be compared with placebo on the key secondary efficacy endpoint using the usual Hochberg procedure with a 2-sided  $\alpha = 0.05$ . If neither arm is superior to placebo on the primary efficacy endpoint, the procedure will stop and the comparison of each atabecestat arm to placebo on the key secondary endpoint will also be ruled not statistically significant. If 1 of the 2 arms is superior to placebo on the primary efficacy endpoint, that arm will be compared with placebo on the secondary efficacy endpoint using a 2-sided  $\alpha = 0.0125$ . The details of the final multiple comparison procedure will be specified in the SAP.

### **11.3.4. Handling of Missing Data**

The impact of the missing data on the efficacy results will be assessed using sensitivity analyses. The follow-up data from subjects who stop taking study medication prematurely and data from relevant external databases will be incorporated in the sensitivity analyses. Methods of missing-data sensitivity analyses will be specified in the SAP.

### **11.3.5. Subgroup Analyses**

If warranted, the treatment effect will be assessed in various subgroups of the study population. The subgroup analyses will be specified in the SAP.

## **11.4. Potential Study Design Modifications**

Some of the study design elements may be modified during the study based on a review of emerging external data, blinded interim aggregated study data, or unblinded interim data.

### **11.4.1. Blinded Sample Size Adjustment**

Blinded interim aggregated study data and external data will be used to assess sample size. Sample size may also be increased to account for dropout rate. There will be no Type I error adjustment for this design modification. Full details will be specified in the SAP.

### **11.4.2. Potential Design Modifications Based on External Data**

Emerging external data (including natural history studies of preclinical AD and available placebo data from interventional trials in preclinical AD) will be analyzed as follows:

- a) The RBANS-PACC components may have superior measurement characteristics in the target population as compared to corresponding PACC components. If supported by external data, PACC components may be substituted for 1 or more of the corresponding RBANS-PACC components in the primary endpoint for this study.
- b) Alternative weighting of the PACC components might improve the sensitivity of the PACC to AD-related cognitive decline. If supported by external evidence, the weighting of the PACC components may be modified to increase sensitivity of the PACC to AD-related cognitive decline.
- c) The timing of the primary endpoint could be moved to 3.5 years. Emerging external data (including natural history studies of preclinical AD and available placebo data from interventional trials in preclinical AD) will be analyzed to determine whether there is already a sufficient decline at 3.5 years. If supported by external data, the time point of the primary endpoint may be changed to 3.5 years.

The DMC will not be involved with any of these modifications, as the DMC may have access to the unblinded study data. Since all of the above potential changes will be carried out in a blinded manner without any knowledge of unblinded study data, there will be no Type I error adjustments. Full details will be specified in the SAP.

#### **11.4.3. Unblinded Interim Analyses to Assess Futility**

The following are the futility IAs, or potential IAs that may lead to a futility IA:

- Futility IA of CSF  $A\beta_{1-40}$
- IAs that may lead to a futility IA of the cognitive endpoints:
  - IA of amyloid PET
  - IA of CSF tau/p-tau
  - IA of tau PET
- Futility IA of cognitive endpoints

$A\beta_{1-40}$  in CSF is expected to be reduced with atabecestat treatment by 50% to 90% at steady-state in a dose dependent manner with an SD of 20%. The DMC may recommend stopping the study if the difference in percentage reduction of CSF  $A\beta_{1-40}$  between the atabecestat 25 mg dose and placebo is <50% at Month 12. Assuming an SD of 20% and 20 subjects per group, there is less than 5% chance of continuing the study if the true percentage reduction at the 25 mg dose is  $\leq 40\%$  and less than a 5% chance of stopping the study if the true percentage reduction at the 25 mg dose is  $\geq 60\%$ .

The DMC may recommend an IA of cognitive endpoints if the percentage amyloid accumulation slowdown (difference in change between placebo and atabecestat dose divided by placebo change) is <10% in the most relevant biomarker (among amyloid PET, CSF tau/p-tau, and tau PET) for both atabecestat dose arms.

Assuming amyloid PET accumulation in 24 months, tau PET accumulation in 18 months and CSF p-tau increase in 12 months in the study population are similar to the amyloid accumulation

data in the ADNI study, a total of at least 168 subjects in the IA analysis set for a given biomarker (56 subjects per group) is expected to provide adequate control of false positive and false negative error for the interim analysis. If the true accumulation slowdown for atabecestat is  $\geq 60\%$ , the probability of a false negative is approximately 10%. If the true accumulation slowdown is  $< 5\%$ , the probability of a false positive is approximately 40%.

There will be no Type I error adjustment for the IAs since no superiority will be declared from any of them. An independent external DMC (see Section 11.11) will review the IA data and make recommendations per prespecified IA decision rules.

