Percent changes from baseline in $A\beta_{1-40}$ in CSF and plasma at Month 12 will be analyzed based on an analysis of covariance (ANCOVA) model that includes treatment group and the baseline value as a covariate. The Least Squares (LS) means and treatment differences versus placebo with the corresponding 95% confidence intervals will be provided.

The criterion for lack of effect on $A\beta_{1-40}$ in CSF is based on the LS mean difference (A-P) in percent reduction from baseline in $A\beta_{1-40}$ between the 25 mg dose (A) and placebo (P):

- If $(A - P) < 50\%$, then conclude lack of effect for atabecestat
- If $(A - P) \geq 50\%$, then do not conclude lack of effect for atabecestat

Where P is the LS mean for percent reduction versus baseline in $A\beta_{1-40}$ in the placebo group, and A is the LS mean for percent reduction versus baseline in $A\beta_{1-40}$ in the 25 mg group.

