Attachment 2: Sample Size Justification for Biomarker Interim Analyses

CSF A β ₁₋₄₀ interim analysis

Twenty subjects per group was chosen to provide adequate control of false positive and false negative error for the interim futility analysis, assuming the SD in each treatment is 20% or less, as shown in the [Figure A1](#) below.

Figure A1: Operating characteristics of the CSF A β ₁₋₄₀ futility criterion

[figure not shown]

Assumptions:

N=20 per group, SD=20%.

Interim analysis of other biomarkers

In the latest Alzheimer's Disease Neuroimaging Initiative (ADNI) database, the (Mean/SD) ratio for change from baseline in amyloid accumulation at Month 24 was around 0.5 in ADNI subjects with positive AV45 amyloid PET baseline status (see **Error! Reference source not found.**). Assuming amyloid PET accumulation in 24 months, tau PET accumulation in 18 months and CSF p-tau increase in 12 months in the study population are similar to the amyloid accumulation data in ADNI, a total of 168 subjects in the IA dataset for each of the biomarkers (56 subjects per group) are expected to provide adequate control of false positive and false negative error for the interim analysis as shown in the [Figure A2](#) below.

Figure A2: Operating characteristics of the futility criterion for amyloid PET

Assumptions:

(Mean/ SD) ratio of change in placebo is 0.5.

2-sample t-test with N=56 per group

% Amyloid Accumulation Slowdown = $(\text{LS mean change in pbo} - \text{LS mean change in active}) / \text{LS mean change in pbo} \times 100\%$

Prob (lack of effect) = Prob (% amyloid accumulation slowdown < cutoff | Assumed % amyloid accumulation slowdown)

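### Protocol 11.4.3 puts both errors of the CSF Aβ1-40 futility rule below 5%, but its own inputs give 5.7% at true differences of 40% and 60%

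*Protocol*

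**What the plan says.** Protocol 11.4.3 allows the DMC to recommend stopping on the basis of the CSF Aβ1-40 results. The trigger is that the contrast in reduction "between the atabecestat 25 mg dose and placebo is <50% at Month 12". It then gives two error rates.

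- Wrongly continuing: "Assuming an SD of 20% and 20 subjects per group, there is less than 5% chance of continuing the study" when the true reduction at 25 mg is 40% or less.
- Wrongly stopping: "less than a 5% chance of stopping the study if the true percentage reduction at the 25 mg dose is" 60% or more.

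SAP 3.1.1 keeps the 50% cut-off for its conclusion about lack of effect. That criterion "is based on the LS mean difference (A-P) in percent reduction from baseline", taken from an ANCOVA with treatment group and baseline value. The rule compares a point estimate with 50%; it involves no test, significance level or confidence limit.

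SAP Attachment 2 justifies the sample size in words only: "Twenty subjects per group was chosen to provide adequate control of false positive and false negative error for the interim futility analysis". The condition it attaches to that claim reads "assuming the SD in each treatment is 20% or less". Its text gives no 5% figure, and its operating-characteristic figure is not reproduced in the available copy.

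**The concern.** The protocol's two rates are strict upper bounds, tied to a stated SD and a stated group size. The ranges they cover include their endpoints, 40% and 60%, so the bounds must hold there. Those endpoints lie only 10 points from the cut-off, and 20 subjects per arm with an SD of 20 points is a little too few for a 10-point margin to give 5% tails.

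These are the only numerical operating characteristics given in the text for this rule. It is also the only planned interim analysis that was carried out (SAP sections 1 and 3). A reader judging how reliable the conclusion is would take them at face value.

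**Working it through.** **Inputs**

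- SD of the percentage reduction: 20 points (Protocol 11.4.3). SAP Attachment 2 applies it to each treatment.
- Group size: 20 per arm (Protocol 11.4.3).
- Rule: stop if the estimated 25 mg minus placebo difference is below 50 points (Protocol 11.4.3; SAP 3.1.1).
- Boundary truths: 40% for wrongly continuing and 60% for wrongly stopping (Protocol 11.4.3).
- Placebo change: none stated. It is taken as zero, so the true reduction at 25 mg equals the true difference.

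**What the stated bound would need**

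A tail below 5% requires z above 1.645, so the standard error must be below 10/1.645 = 6.08 points.

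**What the stated inputs give**

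1. SE = 20 × √(1/20 + 1/20) = 6.32 points, which is above 6.08.
2. z = (50 − 40)/6.32 = 1.581.
3. P(continue, true difference 40%) = 1 − Φ(1.581) = 5.69%.
4. P(stop, true difference 60%) = Φ((50 − 60)/6.32) = 5.69%.
5. A simulation of 200,000 two-arm trials at a true difference of 40% gave 5.63%.

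The protocol's figure is therefore not reproduced.

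**Where the bound does hold**

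50 ± 1.645 × 6.32 = 50 ± 10.40. With these inputs each error is at most 5% for true differences of about 39.6% or less, or 60.4% or more.

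**What would bring the rate at 40% and 60% below 5%** (one change at a time)

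- More subjects: 21 per arm gives 5.26%; 22 per arm gives 4.86%.
- Smaller SD in both arms: 10/(1.645 × √(2/20)) = 19.2 points or less.
- Smaller SD on placebo only: about 18.4 points gives SE = √(20²/20 + 18.4²/20) = 6.08 and an error of 4.99%.
- Baseline adjustment: residual SD = 20 × √(1 − r²). A baseline correlation r of 0.28 gives 19.2 points and 4.98%.
- Placebo mean treated as known: SE = 20/√20 = 4.47 and 1.3%. This does not fit a rule defined as a difference from a placebo arm that has its own SD.

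A non-zero placebo change would not rescue both bounds. It moves the true difference the same way in both scenarios, so one error falls and the other rises.

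**The case against.** The strongest reply is that the hand calculation is simpler than the planned analysis. SAP 3.1.1 adjusts for baseline and sets 20 per group as a minimum, and SAP Attachment 2 treats 20% as an upper limit for the SD. Modest gains from any of these would bring the rates under 5%. This stands as a statement about the analysis actually run: the documents give neither the baseline correlation nor the realised group sizes and SD, so no one can show from them that the actual rates exceeded 5%. It does not repair Protocol 11.4.3, which attaches its bound to an SD of 20% and 20 per group with no further condition.

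Rounding does not help either. The figure of 5.7% rounds to 6%, and the same section uses approximate wording for the other biomarkers' error rates while stating a strict bound here.

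It is also fair to say that little depends on the difference. The modelled median reduction at 25 mg is about 84% (Protocol 3.2.3). With no placebo change that is (84 − 50)/6.32 = 5.4 standard errors above the cut-off, where a wrong stop is negligible on either figure. Dosing has ended, and under SAP 3.1.1 the DMC reports the result without making a recommendation. This limits the importance of the error but does not make the stated bound true.

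**Conclusion.** The strict bound in Protocol 11.4.3 is wrong as written. With its own inputs each error is 5.7% at true differences of 40% and 60%, an excess of 0.7 percentage points. This rests on two independent arms, an SD of 20 points in each, 20 per arm, approximate normality of the means, no placebo change and a point-estimate cut-off.

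A reader might go further in three ways that the documents do not support.

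- **That the rule or the sample size is unsound.** An error of about 6% at 10 points either side of the cut-off is still reasonable for a non-binding futility rule.
- **That the SAP repeats the error.** Attachment 2 claims adequate control without a 5% figure in its text, its figure cannot be judged, and SAP 3.1.1 states only the cut-off.
- **That the interim result is to be reported against the 5% rates.** SAP 3.1.1 plans LS means, differences from placebo, 95% confidence intervals and a comparison with 50%. It does not refer to the 5% rates.

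This is a minor correction to a stated figure.

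**What to change.** In Protocol 11.4.3, replace the two bounds of less than 5% with *about 6% (5.7%) at a true difference of 40% or 60%*, or with *at most about 6%* over the ranges already given. Say that this assumes an SD of 20% in each arm, 20 per arm and no change on placebo.

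SAP 3.1.1 and the text of SAP Attachment 2 need no correction. Attachment 2 could usefully quote the 5.7% beside its verbal claim.

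The cost is wording only: no change to the rule, the sample size, the data collected or the analysis. One planning figure becomes slightly less favourable.

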### 11.5. Pharmacokinetic Analyses

Data will be listed for all subjects with available plasma concentrations per treatment. All concentrations below the limit of quantification (LOQ) or missing data will be labeled as such in the concentration data listings. Concentrations below the LOQ will be treated as zero in the summary statistics. All subjects and samples excluded from the analysis will be clearly documented. Per visit, scheduled time, and dose summary tables of atabecestat plasma concentrations will be presented including descriptive statistics. Actual and/or dose-normalized plasma concentrations will be graphically displayed as a function of dose in order to explore dose proportionality. No formal statistical comparison between doses is planned. The plasma drug concentration-time data collected during the study will be presented graphically as concentrations versus time after the previous dose.

Population PK analysis of plasma concentration-time data of atabecestat will be performed using nonlinear mixed-effects modeling. Data may be combined with those from a selection of Phase 1 or Phase 2 studies in order to support a relevant structural model. Available subject characteristics (eg, demographics, laboratory variables, genotypes) will be tested as potential covariates affecting PK parameters. Descriptive statistics will be used to summarize atabecestat plasma concentrations at each sampling time point and the following PK parameters of atabecestat (estimated using popPK modeling):  $C_{\text{trough}}$  and  $AUC_{\text{tau}}$ . Other PK parameters, if calculated, will also be summarized. Details of the popPK analysis will be provided in a popPK analysis plan and results will be presented in a separate report.

The parameter of interest for the statistical analysis will be the log-transformed estimated dose normalized  $AUC_{\text{tau}}$ . All ratios will be calculated as differences of least square means of the appropriate model on the log-scale, and will be presented after back-transformation to the original scale with the corresponding 90% CIs.

### 11.6. Pharmacokinetic/Pharmacodynamic Analyses

Modeling of clinical scores (eg, PACC) may be performed using population PK/PD or disease progression models. If PK/PD modeling of clinical scores is performed, possible covariates of disease progression and/or treatment effect will be investigated. PK/PD modeling may also be performed to assess exposure- and dose-response relationships of key biomarkers, such as CSF  $A\beta_{1-40}$  concentrations, amyloid, and/or tau PET imaging results. Other biomarkers may be

explored if required. Details of the PK/PD analyses will be described in a population PK/PD analysis plan and results will be presented in a separate report.

### **11.7. Biomarker Analyses**

Statistical analyses will be performed on the following:

- CSF A $\beta_{1-40}$  and plasma A $\beta_{1-40}$
- Amyloid PET parameters
- CSF p-tau
- Tau PET
- Volumetric and task-free functional MRI parameters

In addition to CSF A $\beta_{1-40}$  and CSF p-tau, alternate CSF markers of neurodegeneration will also be analyzed similarly. CSF analyses will be performed using the CSF analysis population.

For amyloid PET, the parameters of key interest will be the global composite ROI SUVR (eg, frontal, medial temporal, or parietal cortices; anterior and posterior cingulates) and regional SUVR (eg, cortical and subcortical ROIs). Amyloid PET analysis will be performed using the amyloid PET analysis population.

For tau PET, the parameters of key interest will be tau PET signal (SUVR) in ROI(s) known to accumulate substantial tau. The analyses will be performed using the tau PET analysis population.

For MRI, the parameters of key interest will be brain volumes of the cortical and sub-cortical regions.

The treatment effect will be estimated and compared with placebo. Details of the statistical methods will be provided in the SAP.

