2.6.4. Biomarker Analysis Sets

The CSF A β analysis set includes all randomized subjects with valid CSF A β data at baseline and at ≥ 1 post-baseline visit. All CSF A β values will be blindly reviewed for qualification.

The amyloid PET analysis set includes all randomized subjects with valid amyloid PET data at baseline and at ≥ 1 post-baseline visit.

The CSF p-tau and t-tau analysis set includes all randomized subjects with valid CSF p-tau and t-tau data at baseline and at ≥ 1 post-baseline visit.

The tau PET analysis set includes all randomized subjects with valid tau PET data at baseline and at ≥ 1 post-baseline visit.

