7.2. Pharmacodynamics

Biomarkers measured in this study include the following:

- Fluid biomarkers

- CSF: A subset of subjects will have longitudinal CSF samples taken during the study at randomization (if a CSF screening sample was taken, it was not necessary to have a repeat sample at randomization), Month 12, Month 36 (or early termination if not collected at the previous visit). After the biomarkers interim analyses (Section 3.1.1), the Month 12 sample could be taken any time between baseline and Month 36. The key parameter of interest is $A\beta_{1-40}$. $A\beta_{1-37}$, $A\beta_{1-38}$, $A\beta_{1-42}$, p-tau, and t-tau will also be measured.
- Imaging biomarkers
 - Amyloid PET: A subset of subjects will have longitudinal amyloid PET scans during the study at randomization (if an amyloid PET scan was performed during screening, it was not necessary to have a repeat scan at randomization), Month 24 and Month 48 (or early termination). The parameters of key interest are the composite region of interest (ROI) SUVR and regional SUVR's.
 - MRI: All subjects will have an MRI during screening and after randomization at Months 6, 12, 24, 36 and 54 (or early termination, if not performed at the previous visit). The parameters of key interest are brain volumes of the cortical and sub-cortical regions.

Biomarker analyses will be based only on those subjects with at least 85% treatment compliance (see Section 4.3) at the analysis time point.

Changes from baseline and percent changes from baseline will be calculated for all parameters.

Values of each parameter will be summarized with descriptive statistics at each time point by treatment group. Change from baseline will also be summarized for each parameter, at each time point by treatment group. Percent change from baseline in CSF and plasma $A\beta_{1-40}$ will be summarized at each time point by treatment group. Plots of mean (\pm SE) values, changes, and/or percent changes over time by treatment group will be provided for selected biomarkers.

For off-treatment visits, change and percent change from the off-treatment baseline (see Section 2.4) may also be calculated and summarized with descriptive statistics.

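### Apart from the Month 12 interim ANCOVA of CSF and plasma Aβ1-40, the SAP plans no between-arm biomarker estimate, although Protocol 11.7 says the effect will be estimated against placebo

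*Protocol*

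**What the plan says.** Protocol 11.7 lists CSF and plasma Aβ1-40, amyloid PET, CSF p-tau, tau PET and MRI. The MRI entry reads "Volumetric and task-free functional MRI parameters". On tau PET it adds: "For tau PET, the parameters of key interest will be tau PET signal (SUVR) in ROI(s) known to accumulate substantial tau". It closes: "The treatment effect will be estimated and compared with placebo", and leaves the methods to the SAP.

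SAP 7.2 lists CSF markers (including p-tau and t-tau), amyloid PET and MRI volumes. Its method is "Values of each parameter will be summarized with descriptive statistics at each time point by treatment group", then "Change from baseline will also be summarized for each parameter, at each time point by treatment group". It also gives percent change for CSF and plasma Aβ1-40, mean plots, and scatterplots against cognition. It names no model, no difference between arms and no interval. It restricts the analyses to subjects with at least 85% compliance. Neither tau PET nor functional MRI appears.

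Elsewhere in the SAP:
- Section 3.1.1 analyses percent change in CSF and plasma Aβ1-40 at Month 12 by ANCOVA on treatment and baseline value: "The Least Squares (LS) means and treatment differences versus placebo with the corresponding 95% confidence intervals will be provided". Section 1 says the CSF Aβ1-40 interim analysis was performed.
- Section 1.1.3 keeps the tau PET and functional MRI objectives.
- Section 2.6.4 still has a tau PET set: "The tau PET analysis set includes all randomized subjects with valid tau PET data at baseline", plus at least one post-baseline visit.
- Section 1 says that after the stop the objectives cannot be evaluated, and that selected efficacy outcomes will be compared between groups. It does not say how biomarkers are treated.

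**The concern.** The protocol passes the biomarker methods to the SAP, and for most of the listed biomarkers the SAP supplies no method that estimates an effect. Several objectives in SAP 1.1.2 and 1.1.3, such as brain volume on MRI and CSF markers of neurodegeneration, ask for a comparison with placebo. As planned, the report would answer them with three unadjusted arm summaries, taken in a subset selected on compliance after randomisation. Readers would have to form the contrast themselves, without baseline adjustment.

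Tau PET scans were taken under separate consent (Protocol 9.4.2.2) and carry radiation exposure (Protocol 16.1). The analysis set defined for them feeds no stated analysis, and a reader cannot tell whether that is a decision or an omission.

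**Working it through.** The plan gives no precision figure for these biomarkers, so the main check sets the text of the two documents side by side. A short calculation then shows what the missing estimates could offer.

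**1. Coverage, biomarker by biomarker**

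| Biomarker in Protocol 11.7 | Between-arm estimate in SAP | Other output in SAP 7.2 |
|---|---|---|
| CSF and plasma Aβ1-40 | Yes, Month 12 interim ANCOVA (3.1.1) | Summaries by arm |
| CSF p-tau (SAP adds t-tau) | None | Summaries by arm |
| Amyloid PET | None | Summaries by arm |
| MRI volumes | None | Summaries by arm |
| Tau PET | None | Not named; set defined in 2.6.4 |
| Task-free functional MRI | None | Not named |

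**2. Does the early stop account for the pattern?**

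The SAP's own cessation figures reproduce: 557/1650 = 33.8% (stated as 34%) and 447/557 = 80.3% (stated as 80%). That leaves 557 − 447 = 110 subjects with more than 12 months of treatment, or 110/3 ≈ 37 per arm if evenly split.

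With those numbers the SAP still plans:
- PACC contrasts against placebo with 95% CIs and p-values at Months 6, 12 and 18 (5.2.3). On-treatment Month 18 data can come only from the 110, so from at most about 37 per arm on an even split.
- Similar mixed models for CFI (5.3.2) and for RBANS and ADCS-ADL-PI (5.4.2).
- Optional inferential analyses for exploratory efficacy variables (5.5.2).
- An Aβ1-40 ANCOVA sized at 20 per group (3.1.1).

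Where the SAP withdraws an analysis, it usually says so: PK parameters (7.1), PK/PD relationships (7.3) and the other interim analyses (1 and 3). No such statement covers tau PET, functional MRI or the comparison promised in Protocol 11.7.

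**3. Precision of the missing estimates**

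For two arms of n subjects, in SD units of the change score and before any gain from baseline adjustment:

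SE = √(2/n); 95% CI half-width ≈ 1.96 × √(2/n)

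| n per arm | Basis | SE (SD) | Half-width (SD) |
|---|---|---|---|
| 100 | Assumption, Month 6 MRI | 0.14 | 0.28 |
| 37 | 110/3, Month 12 | 0.23 | 0.46 |
| 20 | Planned size of the CSF interim analysis | 0.32 | 0.62 |

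The documents do not give the number of subjects with any post-baseline biomarker result. At Month 12, 37 per arm is only a guide. The SAP window (Days 334 to 410) admits some subjects treated for slightly less than a year, while missing visits and the 85% compliance rule remove others.

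**The case against.** The strongest reply is that this is a disclosed reduction. The SAP was amended because dosing stopped, says the objectives cannot be evaluated, and limits comparisons to selected efficacy outcomes. Protocol 11.7 leaves the methods to the SAP and promises neither baseline adjustment nor intervals. The first scheduled post-baseline tau PET is at Month 18 and the first amyloid PET at Month 24, while no subject had more than 27 months of treatment. Fitting models to so few scans would add little. If the summaries show n, mean and SD, a crude difference can be worked out from them.

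Much of this stands. Describing sparse PET data by arm is defensible, and the early stop is a genuine reason. It does not reach MRI, which is scheduled for all subjects at Months 6 and 12, or CSF markers at Month 12, because the SAP keeps adjusted contrasts elsewhere on similar or smaller numbers. A general statement about cessation also does not tell the reader which Protocol 11.7 comparisons were withdrawn.

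Four stronger readings are tempting, and the documents do not support them:
- *No biomarker gets an adjusted estimate.* SAP 3.1.1 provides one, with a 95% CI, for CSF and plasma Aβ1-40 at Month 12.
- *Tau PET has been dropped from the SAP.* The objective and the analysis set remain. The list in 7.2 is also not exhaustive: plasma Aβ1-40 is summarised there without being listed. What is missing is a stated analysis.
- *The SAP gives no reason for doing less.* It does; the reason is general and does not mention biomarkers.
- *Month 12 data would be nearly as precise as Month 6.* With about 37 per arm treated beyond 12 months, that cannot be assumed.

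**Conclusion.** The point holds in this limited form. Beyond the interim Aβ1-40 ANCOVA, the SAP contains no between-arm estimate for MRI volumes, CSF p-tau and t-tau, or amyloid PET, and no stated analysis for tau PET or functional MRI. This falls short of Protocol 11.7. The early stop explains a smaller analysis but does not by itself justify this gap.

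The consequence is moderate. No confirmatory conclusion is affected, since the SAP treats all comparisons as exploratory. What is lost is an interpretable effect estimate from data already collected. The half-widths of 0.28 SD and 0.46 SD rest on an assumed 100 per arm at Month 6 and an even split of 110 subjects at Month 12. The true counts could move either figure in either direction.

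**What to change.** In SAP 7.2:
1. For biomarkers and on-treatment visits with enough data, chiefly MRI volumes at Months 6 and 12 and CSF markers at Month 12, add an ANCOVA of change (or percent change) from baseline with the baseline value as covariate. An MMRM is suitable for MRI volumes. Report LS mean differences from placebo with 95% CIs, labelled exploratory and without multiplicity adjustment, in line with SAP 5.1.1.
2. Add a summary of tau PET SUVR in the set already defined in SAP 2.6.4, and of functional MRI parameters if available.
3. Keep sparse amyloid and tau PET visits descriptive, and state that this departs from Protocol 11.7 and why.
4. Show the number of subjects per arm beside every estimate.

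The cost is a few extra tables and no new data. The ANCOVA has the same form as in SAP 3.1.1, but that analysis was assigned to the independent statistical support group, so some programming should be expected. The downside is wide intervals, in a subset selected on compliance, that must be read as exploratory.
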